- No evidence of QT interval prolongation (based on a study-specific power model and Fridericia's correction methods) was found in participants treated with intranasal or IV esketamine in a thorough corrected QT interval (QTc) study. Moxifloxacin demonstrated QTc prolongation and established assay sensitivity.
- Treatment with intranasal esketamine does not appear to be associated with development of potential psychotic-like symptoms. No intervention-emergent AEs of psychosis were reported across the Phase 2 and 3 studies in TRD. Mania was reported in 2 esketamine-treated participants (1 report after first dose of esketamine and oral AD [duloxetine] and second report during the follow-up phase), and hypomania was not reported in any participant.
- No cases of interstitial cystitis or ulcerative cystitis have been reported with esketamine use in any of the completed or ongoing studies, including the ongoing long-term open-label TRD study TRD3008, where over 700 participants were treated for at least 2 years. There was a higher rate of cystitis-related intervention-emergent AEs (eg, pollakiuria, dysuria, micturition urgency) with esketamine compared to placebo.
- No cases of newly elevated total serum bilirubin to >2x the upper limit of normal associated with esketamine treatment were identified. No cases in any Phase 1, 2, or 3 esketamine studies across indications met the criteria for severe drug-induced hepatocellular injury as defined by Hy's law. No new hepatic safety signal was observed in the ongoing long-term open-label TRD study TRD3008, where over 700 participants were treated for at least 2 years.
- Nasal tolerability in participants self-administering esketamine nasal spray, including that
 following long-term treatment, was good. There were no nasal examination findings or Nasal
 Symptom Questionnaire evidence to support an impact on nasal anatomy or function including
 the sense of smell.
- Ketamine, the racemic mixture of arketamine and esketamine, has been reported as a drug of
 abuse. The potential for abuse, misuse, and diversion of intranasal esketamine is minimized
 due to the product's design and the administration taking place under the supervision of a
 healthcare professional. Evidence of abuse, misuse, and diversion was not observed in clinical
 studies of intranasal esketamine.

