- Cystitis: adenoviral hemorrhagic cystitis; allergic cystitis; bladder candidiasis; bladder diverticulitis; cystitis bacterial; cystitis erosive; cystitis escherichia; cystitis glandularis; cystitis gonococcal; cystitis helminthic; cystitis hemorrhagic; cystitis interstitial; cystitis klebsiella; cystitis noninfective; cystitis pseudomonal; cystitis radiation; cystitis ulcerative; cystitis viral; emphysematous cystitis; eosinophilic cystitis; fungal cystitis; lupus cystitis; malacoplakia vesicae; schistosomiasis bladder; trigonitis; tuberculosis bladder; urinary bladder abscess; viral hemorrhagic cystitis
- **Hepatic impairment**: acquired complement deficiency disease; bilirubin excretion disorder; crigler-najjar syndrome; HELLP (hemolysis, elevated liver enzymes, and a low platelet count) syndrome; hepatic function abnormal; hyperammonemic crisis; hyperammonemia; hypertransaminasemia; hypoalbuminemia; hypoproteinemia

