9.4.5. Safety Analyses

All safety analyses will be made on the Safety/Efficacy Population.

Adverse Events

The verbatim terms used in the eCRF by investigators to identify adverse events will be coded using the Medical Dictionary for Regulatory Activities (MedDRA). Any AE occurring at or after the initial administration of study intervention through the day of last dose plus 30 days is considered to be intervention-emergent. All reported intervention-emergent adverse events will be included in the analysis. For each adverse event, the percentage of participants who experience at least 1 occurrence of the given event will be summarized.

Intervention-emergent AEs of special interest will be summarized separately grouped in the categories as described in Section 8.3.6.

Summaries, listings, or participant narratives may be provided, as appropriate, for those participants who die, who discontinue intervention due to an adverse event, or who experience a serious adverse event.

Clinical Laboratory Tests

Only clinically relevant changes in laboratory parameters that meet the definition of an AE during the study are reported by the investigator as AEs and these will be included in the all intervention-emergent AE analyses.

Vital Signs

Descriptive statistics of pulse/heart rate, respiratory rate, and supine blood pressure (SBP and DBP) values and changes from Study TRD3013 baseline will be summarized at each scheduled time point. The percentage of participants with values beyond clinically important limits will be summarized.

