10.7.1. Patient Health Questionnaire-9 (PHQ-9)

10.7.2. European Quality of Life (EuroQol) Group, 5-Dimension, 5-Level (EQ-5D-5L)

10.8. Appendix 8: Clinical Laboratory Tests

The following tests will be performed according to the Schedule of Activities by the local laboratory:

Protocol-Required Safety Laboratory Assessments

Laboratory	Parameters		
Assessments Hematology	-hemoglobin	-white blood cell (WBC) count with	
Trematology	-nemogloom	differential	
	-hematocrit	-platelet count	
	-red blood cell (RBC) count	platelet count	
Clinical	-sodium	-aspartate aminotransferase (AST)	
Chemistry	-potassium	-alanine aminotransferase (ALT)	
(fasting, at	-chloride	-gamma-glutamyltransferase (GGT)	
least 8 hours)	-bicarbonate (optional) ^a	-alkaline phosphatase	
	-blood urea nitrogen (BUN)	-creatine phosphokinase (CPK)	
	-creatinine	-calcium	
	-glucose	-phosphate	
	-total cholesterol	-albumin	
	-high-density lipoprotein cholesterol	-total protein	
	-triglycerides	-total bilirubin	
	-low-density lipoprotein cholesterol		
Routine	Dipstick	Sediment (if dipstick result is abnormal)	
Urinalysis	-specific gravity	-red blood cells	
	-рН	-white blood cells	
	-glucose	-epithelial cells	
	-protein	-crystals	
	-blood	-casts	
	-ketones	-bacteria	
	-bilirubin		
	-urobilinogen		
	-nitrite		
	-leukocyte esterase		
Pregnancy Tests	Urine pregnancy testing for wom Activities and Section 8.2.4	en of childbearing potential only; see Schedule of	

^a Bicarbonate assay is optional, based on availability of the test at the local laboratory.

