Incidence of treatment-emergent AEs of special interest will be summarized, grouped in the following MedDRA-based categories: sedation, dissociation, suicidality, suggestive of abuse potential, cystitis and hepatic impairment. See Appendix 7 for a list of AEs in each category.

CONFIDENTIAL – FOIA Exemptions Apply in U.S.

A listing of participants who died will be provided.

Duration of TEAE

Additionally a bar chart will be created to present the duration of AEs (Treatment-emergent AEs in more than 5% of patients).

Duration of AEs will be calculated as:

- If AE start date = AE end date: AE end time AE start time
- If AE start date < AE end date: AE end date AE start date +1
- Note: for AE with outcome FATAL: AE end date= death date

AEs are categorized in following categories

- Duration: <= 1hour
- Duration: > 1 hour to <= 2 hours
- Duration: > 2 hours to <= 3 hours
- Duration: > 3 hours to <= 8 hours
- Duration: > 8 hours but AE start date=AE end date
- Unknown: Missing duration (ie. missing start or end time) and AE start date=AE end date
- Duration: 2 days to <= 7 days
- Duration: 8 days to <=28 days
- Duration: >28 days or AE ongoing

Bar chart that shows the percentage of AEs in each category is created.

Clinically significant weight change

- Calculate the number and % of patients with an increase of at least 7% in body weight at any point in time compared to baseline. Only include visits until last dose + 14 days.
- Calculate the number and % of patients with a decrease of at least 7% in body weight at any point in time compared to baseline. Only include visits until last dose + 14 days.
- Above proportions are calculated on all patients in the safety analysis set who have baseline and at least one post-baseline body weight measurement.
- If body weight missing, assume no 7% increase/decrease from baseline.

Medication

- Calculate the number and % of patients who received any concomitant therapy for TEAE. Denominator is patients in safety analysis set with at least one TEAE.
- Calculate the number and % of patients who received any concomitant therapy for TEAE, by preferred term. Denominator is patients in safety analysis set who developed the specific preferred term as TEAE.

• Analyses are based on data on AE page (AECONTRT). If AECONTRT is missing, assume no concomitant therapy received.

Days with AE

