5.6.3. Additional Safety Assessments

5.6.3.1. Clinical Laboratory Tests

Clinically significantly abnormal laboratory results are recorded as an AE and will be reported in Section 5.3.2.

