Cystitis	schistosomiasis bladder
Cystitis	trigonitis
Cystitis	tuberculosis bladder
Cystitis	urinary bladder abscess
Cystitis	viral hemorrhagic cystitis

AE Special Interest Category	Preferred Term
Hepatic impairment	acquired complement deficiency disease
Hepatic impairment	bilirubin excretion disorder
Hepatic impairment	crigler-najjar syndrome
Hepatic impairment	HELLP (hemolysis, elevated liver enzymes, and a low platelet
	count) syndrome
Hepatic impairment	hepatic function abnormal
Hepatic impairment	hyperammonemic crisis
Hepatic impairment	hyperammonemia
Hepatic impairment	hypertransaminasemia
Hepatic impairment	hypoalbuminemia
Hepatic impairment	hypoproteinemia

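### The closed hepatic AESI list has no analyte-named laboratory-increase term and no hepatitis or liver-injury term, so the grouped hepatic count may be too low

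*Protocol*

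**What the plan says.** AESIs belong to the primary endpoint (protocol section 3), and hepatic impairment is one of six AESI categories. Protocol 8.3.6 lists its terms, beginning "acquired complement deficiency disease; bilirubin excretion disorder; crigler-najjar syndrome", followed by HELLP syndrome and then "hepatic function abnormal; hyperammonemic crisis; hyperammonemia; hypertransaminasemia; hypoalbuminemia; hypoproteinemia". SAP Appendix 7 repeats the list in a preferred-term column, and SAP 5.3.2.1.1 makes that appendix the definition of each category: "See Appendix 7 for a list of AEs in each category". Neither document provides a broader search, a catch-all or a medical review that could add an event to a category.

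The clinical chemistry panel in protocol Appendix 8 includes ALT, AST, GGT, alkaline phosphatase and total bilirubin. Protocol 9.4.5 restricts what reaches the analysis: "Only clinically relevant changes in laboratory parameters that meet the definition of an AE during the study are reported by the investigator as AEs". SAP 5.6.3.1 agrees: "Clinically significantly abnormal laboratory results are recorded as an AE", and refers to the AE section for reporting. Neither document plans a table of laboratory values, shifts or multiples of the upper limit of normal.

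**The concern.** An AESI category gathers related events that would otherwise be scattered over many preferred terms, so that one number can be read for one kind of harm. Here the number depends on matching a coded term to a fixed list. Two participants with the same raised ALT could be treated differently. One recorded as hypertransaminasemia is counted; one recorded under the name of the analyte is not.

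The protocol's own account of hepatic safety (2.2.3.4) is framed in laboratory terms, such as "No cases of newly elevated total serum bilirubin to >2x the upper limit of normal", and in terms of hepatocellular injury under Hy's law. The list has no direct counterpart to either. A low hepatic count could therefore be read as reassurance over as much as 32 + 104 = 136 weeks of exposure when part of it reflects how the category was built. The same list also feeds the AESI listing and the extension-only AESI table in SAP 5.3.2.1.3, so a gap in it carries through to both.

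**Working it through.** There is no stated figure to reproduce. The check sets the lists against the tests performed and the route by which results are reported.

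**1. Do the two lists agree?** Term by term, protocol 8.3.6 has 10 hepatic terms and SAP Appendix 7 has 10, and all 10 match. The gap is therefore common to both documents and is not a transcription error in one.

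**2. What does the list hold for each liver test?**

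| Test collected | Term naming an increase in it | Nearest listed term |
|---|---|---|
| ALT | none | hypertransaminasemia |
| AST | none | hypertransaminasemia |
| GGT | none | hepatic function abnormal (general) |
| Alkaline phosphatase | none | hepatic function abnormal (general) |
| Total bilirubin | none | bilirubin excretion disorder (related, but not a raised value) |

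A word search of the ten terms finds nothing for alanine, aspartate, gamma, alkaline, increased or jaundice. Liver and enzyme occur only inside the expansion of HELLP. No term is for hepatitis or liver injury.

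**3. How often are the tests done?** The Schedule of Activities has laboratory tests every 24 weeks, at Week 104 or end of study, and at safety follow-up. Over the full 104 weeks that is Weeks 24, 48, 72 and 96 (4 visits) + 1 + 1 = up to 6 extension visits.

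**4. By what route does an abnormal result reach the report?** The value is judged clinically relevant, recorded as an AE and coded in MedDRA. It then enters (a) the general treatment-emergent AE tables, whatever the term, and (b) the hepatic category, only if the coded term is one of the ten. Under an analyte-named term it contributes to (a) and adds 0 to (b).

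**5. Is an analyte-named term realistic?** The documents do not give the coding conventions. Protocol 2.2.3.4 does report a measured abnormality in earlier studies as blood pressure increased, so terms of the form parameter-plus-increased have been used in this programme.

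**6. Scale, for illustration only.** The documents give no rate. Let p be the assumed proportion of participants with a liver AE coded under an analyte's name and no listed hepatic term. Let n be the expected enrolment of 100 to 200 (protocol 9.2). The expected number uncounted is n × p, and the chance of at least one is 1 − (1 − p)^n.

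| n | p | Expected uncounted | Chance of at least one |
|---|---|---|---|
| 100 | 1% | 1 | 1 − 0.99^100 = 0.63 |
| 100 | 5% | 5 | 1 − 0.95^100 = 0.99 |
| 200 | 1% | 2 | 1 − 0.99^200 = 0.87 |
| 200 | 5% | 10 | 1 − 0.95^200 > 0.99 |

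**The case against.** The strongest reply is that the list does give raised liver tests a way in. Hypertransaminasemia covers the class to which ALT and AST belong, hepatic function abnormal can take a non-specific liver finding, and bilirubin has a related term. This stands. A reader might infer that the list has no term at all for raised transaminases, or that a liver signal would be lost. The documents support neither reading: the first is contradicted by the list itself, and the second depends on coding decisions that the documents do not show.

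The second reply is that nothing disappears. SAP 5.3.2.1.1 includes all reported treatment-emergent AEs, with number, proportion and incidence rate for each, and adds tables by severity and relationship as well as listings of serious AEs and of AEs leading to discontinuation. SAP 5.3.2.1.3 repeats the table by system organ class and preferred term for the extension alone. This also stands, and it limits the consequence. It does not repair the grouped count, because in those tables liver events stay spread over separate terms.

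Third, the study tests no hypothesis, so no formal conclusion turns on the hepatic count. Protocol 2.2.3.4 also reports no Hy's law cases and no new hepatic signal in an ongoing extension in which over 700 participants were treated for at least 2 years. Both points lower the stakes. Neither bears on whether the category counts what its name suggests.

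The presence of rare conditions such as acquired complement deficiency disease or HELLP on the list is no argument either way, since extra terms do not cause an undercount.

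**Conclusion.** The point holds as one of list completeness. All five liver tests lack an analyte-named increase term, GGT and alkaline phosphatase have no term of their own, and hepatitis and liver injury are absent. Since AEs are the only reporting route for laboratory results, the planned hepatic AESI count may be too low.

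The size cannot be fixed from the documents. It is zero if every such AE is coded to one of the ten listed terms. Under the assumed 1% to 5%, it is 1 to 10 participants across the expected enrolment range. The conclusion assumes that the category is applied as a strict match to Appendix 7, as written, and that at least some liver AEs are coded under an analyte's name or as hepatitis or liver injury. It is a modest correction to one summary within the primary safety analysis. It is not evidence that liver events would go unreported.

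**What to change.** Extend the hepatic list in SAP Appendix 7 with the coded terms for increased ALT, AST, GGT, alkaline phosphatase, transaminases and blood bilirubin, and for hepatitis and liver injury. Because the study is open-label, take the terms from the coding dictionary, not from events already seen.

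Protocol 8.3.6 carries the same ten terms, so record the departure in SAP Appendix 2, which at present mentions only the dropped interim analysis. Report the hepatic AESI count on the extended list with the original ten-term count alongside, so that a reader can see what the extension adds.

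This uses AEs already coded and needs no new data or change in conduct. The cost is a small amount of extra programming and a possibly higher hepatic AESI count. It does not bring in values that the investigator did not record as AEs.

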8.4. Pharmacokinetics

Not applicable.

8.5. Genetics and Pharmacogenomics

Genetics or Pharmacogenomics are not evaluated in this study.

8.6. Biomarkers

Biomarkers are not evaluated in this study.

8.7. Immunogenicity Assessments

Immunogenicity is not evaluated in this study.

9. STATISTICAL CONSIDERATIONS

Statistical analysis will be done by the sponsor or under the authority of the sponsor. A general description of the statistical methods to be used to analyze the efficacy and safety data is outlined below. Specific details will be provided in the Statistical Analysis Plan.

9.1. Statistical Hypotheses

Due to the design of the study (single-arm, long-term extension) and the objective (exploratory nature) no hypothesis is described for this study.

9.2. Sample Size Determination

As no hypothesis is specified for this study, no sample size estimation is performed. Sample size will be driven by pragmatic considerations. It is expected that from 100 to 200 participants will be enrolled in this study.

9.3. Populations for Analysis Sets

For purposes of analysis, the following populations are defined:

Population	Description	
Enrolled	All participants who sign the ICF	
Safety/Efficacy	All participants who take at least 1 dose of study intervention.	

9.4. Statistical Analyses

9.4.1. General Considerations

Descriptive analyses will be performed on the Safety/Efficacy analysis set.

All continuous variables will be summarized using descriptive statistics, which will include the number of participants, mean, standard deviation, median, minimum, maximum, and 95% confidence interval. All categorical variables will be summarized using frequencies and percentages. Distribution of time-to-event variables will be estimated using standard survival analysis methods, including Kaplan-Meier product-limit survival curves. The median time to event with 2-sided 95% confidence intervals will be estimated.

For continuous/ordinal parameters (eg, MADRS, CGI-S, PHQ-9, EQ-5D-5L) descriptive statistics of the observed values and change from Study TRD3013 baseline will be provided for each study visit. For categorical/dichotomous parameters descriptive statistics of the observed score will be provided for each study visit.

9.4.2. Primary Endpoints

For the analysis of adverse events, see Section 9.4.5.

The 10 items of the C-SSRS and the derived endpoints (Suicidal ideation, Suicidal behavior, Suicidal ideation or behavior, Suicidal ideation score) will be summarized as frequency distributions for each assessment during treatment.

9.4.3. Secondary Endpoints

For the MADRS (total and individual scores), CGI-S, and the PHQ-9 (total score), the scale score and changes from Study TRD3013 baseline will be analyzed by study visit.

Frequency of relapse and time to relapse will be described.

For the EQ5D-Health-Utility and the EQ5D-VAS, the score and changes from Study TRD3013 baseline will be analyzed by study visit.

9.4.4. Exploratory Analyses

In cases where the oral AD is switched to another compound from the SNRI/SSRI classes, the impact of switching will be explored. The reasons for the switches will be summarized, the impact on existing AEs will be described, and new AEs starting after the switches will be tabulated. Also, the impact on the efficacy parameters MADRS and CGI-S will be explored by summarizing the

observed values at the visit when the switch was made and changes from that visit at subsequent visits.

9.4.5. Safety Analyses

All safety analyses will be made on the Safety/Efficacy Population.

Adverse Events

The verbatim terms used in the eCRF by investigators to identify adverse events will be coded using the Medical Dictionary for Regulatory Activities (MedDRA). Any AE occurring at or after the initial administration of study intervention through the day of last dose plus 30 days is considered to be intervention-emergent. All reported intervention-emergent adverse events will be included in the analysis. For each adverse event, the percentage of participants who experience at least 1 occurrence of the given event will be summarized.

Intervention-emergent AEs of special interest will be summarized separately grouped in the categories as described in Section 8.3.6.

Summaries, listings, or participant narratives may be provided, as appropriate, for those participants who die, who discontinue intervention due to an adverse event, or who experience a serious adverse event.

Clinical Laboratory Tests

Only clinically relevant changes in laboratory parameters that meet the definition of an AE during the study are reported by the investigator as AEs and these will be included in the all intervention-emergent AE analyses.

Vital Signs

Descriptive statistics of pulse/heart rate, respiratory rate, and supine blood pressure (SBP and DBP) values and changes from Study TRD3013 baseline will be summarized at each scheduled time point. The percentage of participants with values beyond clinically important limits will be summarized.

9.5. Interim Analysis

An interim analysis may be performed after approximately 50 participants have been enrolled in the study, when data have been accrued over a period of 9 to 12 months. The scope of the interim analysis will be developed and documented in a statistical analysis plan.

Other interim analyses may be planned based on specific questions from the medical field or from health authorities in certain countries.

SUPPORTING DOCUMENTATION AND OPERATIONAL CONSIDERATIONS 10.

10.1. **Appendix 1: Abbreviations and Definitions**

AD antidepressant adverse event ΑE

AUC area under the plasma concentration-time curve

area under the plasma concentration-time curve from time 0 to infinity AUC_{∞}

CADSS Clinician-Administered Dissociative States Scale

CGI-C Clinical Global Impression - Change maximum plasma concentration C_{max} COVID-19 Coronavirus Disease 2019

C-SSRS Columbia-Suicide Severity Rating Scale

CYP cytochrome P450, with any appended letters (2B6, 3A4, etc) indicating subtypes

DBP diastolic blood pressure

DSM-5 Diagnostic and Statistical Manual of Mental Disorders, fifth edition

electronic case report form eCRF electronic data capture eDC

European Quality of Life (EuroQoL) Group, 5-Dimension, 5-Level (questionnaire) EQ-5D-5L

EuroQoL Group: visual analogue scale **EO-VAS**

Food and Drug Administration FDA Freedom of Information Act **FOIA GCP** Good Clinical Practice

HC1 hydrochloride

Investigator's Brochure IΒ **ICF** informed consent form

International Committee of Medical Journal Editors **ICMJE**

International Council on Harmonisation **ICH**

IEC Independent Ethics Committee IRB Institutional Review Board

IV intravenous

IWRS interactive web response system

Montgomery-Asberg Depression Rating Scale **MADRS**

major depressive disorder **MDD**

patients with major depressive disorder who have active suicidal ideation with intent **MDSI**

Medical Dictionary for Regulatory Activities MedDRA

N-methyl-D-aspartate receptor **NMDAR** Patient Health Questionnaire, 9-item PHQ-9

product quality complaint **PQC** patient-reported outcome **PRO** corrected QT interval QTc serious adverse event SAE SBP systolic blood pressure

SmPC Summary of Product Characteristics serotonin-norepinephrine reuptake inhibitor **SNRI** selective serotonin reuptake inhibitor SSRI

SUSAR suspected unexpected serious adverse reaction

treatment-resistant depression TRD

Definitions of Terms

Electronic source Contains data traditionally maintained in a hospital or clinic record to document medical system

care or data recorded in a case report form as determined by the protocol. Data in this

system may be considered source documentation.

PRO Reports directly from the participant without interpretation by clinician or anyone else

